- All participants will be encouraged to contact the study site if any episodes of severe hypoglycemia, hyperglycemia, or hospitalizations of any nature occur. In addition, physicians will be asked to notify the study site of any hospitalizations or severe episodes of hypoglycemia or hyperglycemia. Conversely, if the UTHSC Health Hub personnel uncover a morbid event in a study participant, the study staff will contact the participant's personal health care provider. The participants will have access to study personnel or to one of the physician investigators by telephone 24 hours each day through the on-call system in the event of medical problems related to the study. Our health systems have on-call systems that give the participants access to a physician investigator 24 hours a day. To further ensure participant safety, during the follow-up period we plan to assess wellbeing by physical assessment including blood pressure.

**F3a. Adverse Events.** We define serious adverse events as any adverse event or adverse reaction that results in death, is life-threatening, requires hospitalization or prolongation of existing hospitalization, results in persistent or significant disability or incapacity, or congenital anomaly or birth defect. We define adverse events as any untoward medical occurrence in a participant or experimental investigation subject administered a study treatment and which does not necessarily have a causal relationship with this treatment. Because this is a pragmatic trial with minimal risks we will only be recording and reporting serious adverse events such as severe hypoglycemia, or less serious, hyperglycemia.

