**F3b. Classification of Events.** In this study, the likelihood of serious adverse events associated with the planned interventions is very low, and mostly consists of a small possibility of serious hypoglycemic or hyperglycemic reactions associated with improvements in health habits as detailed below. All adverse events will be classified as to whether they are serious or not serious. An adverse event is considered serious if it is life threatening, prolonged or permanently disabling, requires or prolongs hospitalization for any cause other than routine delivery, is a congenital anomaly, or a major cardiovascular event. An event may also be considered serious if an investigator judges it to be a significant hazard or contraindication to continued study intervention or use of study medication. In addition, we will classify all adverse events regarding the relationship, severity, and expectedness as described below.

**Relationship** The following are expected adverse events that may occur during the trial:

**Related to Intervention.** Potential adverse events (AE) known to be associated with caloric restriction, weight loss, or improved medication adherence in patients with diabetes: hypoglycemia, hyperglycemia, malnutrition, bone loss, gall bladder disease. The DiRECT trial which employed a similar intervention found that severe hypoglycemia occurred between 0.2 to 0.57 times per 100 patient years in the treatment arm over the first 4 years of the study. Potential AE's known to be associated with exercise in patients with diabetes: hypoglycemia, fracture or other injury, cardiac arrhythmia, cardiovascular event.

**Related to condition under study.** Potential AE's known to be associated with overweight or obesity include: diabetes, hypertension, dyslipidemia, cardiovascular disease (CVD), gall bladder disease, liver disease. All patients will be monitored at every data collection visit through the 12-month visit for the occurrence of these adverse events.

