## **G. Ethical Considerations.**

**G1. Informed Consent.** The consent process will take place at the beginning of the baseline appointment. We will allow time for discussion or questions about the study. Consent will be obtained by study personnel trained in the consent process. To be able to participate in the study, participants must be adults without impaired decision-making ability that are able to speak, read, and understand English. The consent process will include a discussion of the participant's understanding of what their participation in the study means, which will include, discussion of their rights, the protocol, all potential risks and benefits, and their options and contacts to express any concerns or complaints. A copy of the consent form has been provided with this application.

**G2. Risks and Side Effects.** Possible risks for being in this study include hypoglycemia, gallstones, temporary discomfort, or mental anguish adapting to the behavioral changes (i.e., new diet, increased movement and activity), and possibly breach of confidentiality and privacy by other participants during nutrition education classes. We will have procedures in place to minimize the potential for risks and side effects for participants.

- A possible side effect, Hypoglycemia, is a condition in which an individual's blood sugar (glucose) level is lower than the standard range. Participants will be carefully monitored and counseled on ways to decrease the risk of hypoglycemia. Staff and patients will be trained to recognize the signs and symptoms of hypoglycemia, in addition, a physician is available to provide supervised medication discontinuation for every participant.
- Gallstones are expected to be very rare (Less than 1% risk). However, this discomfort usually resolves or greatly diminishes within one week as long as participants stick with their healthy diet. This potential risk is not serious and is completely reversible. Participants will be carefully monitored and counseled on ways to decrease the risk of gallstones.
- Regarding discomfort and mental anguish, participants will be advised of the risks and benefits of participation and informed of their right to withdraw from the study at any time if they should choose to discontinue. Finally, participants will be advised on informed consent and their role in protecting the confidentiality and privacy of other participants and their own.

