- Randomization: Although it is expected that both study treatments will be either beneficial or neutral (with no effect at all), it is possible that the treatment that a participant is assigned to, may later be shown to be less effective than other therapies.

**G3. Benefits.** Participants may or may not benefit from participating in the study. Benefits that may occur include weight loss and/or diabetes remission. Another tangible benefit for the experimental group is receipt of food subsidies during the study timeframe, while the control group will receive food vouchers. Societal benefits include providing evidence to support the use of multi-component behavioral change interventions to treat obesity and diabetes. Additionally, this research will contribute to a growing body of research on treating diabetes and other chronic illnesses using the 'food as medicine' hypothesis or medically-tailored meals as an alternative to traditional treatment.

**G4. Alternatives to Participation.** Should individuals choose not to participate, they have the option of standard care through options already available to them. Another alternative to participation is the health hub, where health coaches provide support in weight loss, blood pressure control, healthy eating strategies, physical activity, and medication adherence.

**G5. Costs to Subjects.** Costs to subjects include time investment and transportation expenses, but participants can be helped with free medical transportation. Economic burden to subjects includes the time needed for screening and study participation. Regarding the time commitment, we will do our best to work with subjects' schedules, so that any possibly resource-vulnerable individuals are not required to miss work or other important obligations in exchange for their participation. While there is no cost to participation in the study, if participants elect to receive motivational text messages, standard texting rates will apply.

**G6. Compensation to Subjects.** Although there are many potential benefits to participation, subjects will not receive monetary compensation outside of the food subsidies, food vouchers, and transportation expenses (as needed).

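### G2 calls gallstones not serious in advance, against the protocol's outcome-based definition of seriousness, and conflicting recording rules may leave milder gall bladder events unrecorded

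*Combined protocol and SAP*

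**What the plan says.** G2 (Risks and Side Effects) names gallstones as a study risk of under 1%. The same bullet continues that "this discomfort usually resolves or greatly diminishes within one week as long as participants stick with their healthy diet", and closes with "This potential risk is not serious and is completely reversible". The later randomization bullet in G2 says that "it is expected that both study treatments will be either beneficial or neutral".

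F3a defines a serious adverse event by its result: death, threat to life, hospitalization, disability or birth defect. It then says that, the risks being minimal, "we will only be recording and reporting serious adverse events such as severe hypoglycemia", adding hyperglycemia as a less serious example.

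F3b repeats a largely outcome-based definition, lets an investigator also judge an event serious, and says every adverse event is to be classed as serious or not. Among events "known to be associated with caloric restriction, weight loss, or improved medication adherence in patients with diabetes" it lists "hypoglycemia, hyperglycemia, malnutrition, bone loss, gall bladder disease". Gall bladder disease appears again among events related to overweight or obesity ("dyslipidemia, cardiovascular disease (CVD), gall bladder disease, liver disease"), and that paragraph commits to monitoring for the listed events at every data collection visit to month 12.

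F2d says the safety reports will hold data on all adverse events. F2d and F3c both have participants asked at each study visit about emergency and hospital visits, with the answers entered in the database.

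**The concern.** G2 attaches a seriousness grade to a diagnosis; F3a and F3b attach it to the course of each event. Staff and participants are given two incompatible accounts of the same risk. The recording rule in F3a turns on that grade, so whether a gall bladder event enters the database can depend on which section is followed.

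At stake are the risk statement on which the consent discussion draws, and the completeness of the harm data for a listed risk of an intervention built on a diet of about 800 to 1200 kcal/d (C5a, C5d). In a pilot with 36 per arm, harms will be few and each one carries weight in planning a larger study.

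**Working it through.** The plan has no figure here that can be reproduced: the gallstone risk in G2 comes without source, denominator or time window. The check is mainly a comparison of text.

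**1. Seriousness.** Take a gallstone event that leads to admission. Under F3a and F3b it is serious. Under G2 it is not. Both cannot be applied. Now take an event with no admission, no threat to life, no disability and no investigator judgment of hazard. It is non-serious under all three sections. So the contradiction over grading concerns the graver events, while the recording gap (step 3) concerns the milder ones.

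**2. The sentence on discomfort.** The bullet moves from gallstones to a discomfort not mentioned before in that bullet. G2's opening sentence lists temporary discomfort as a risk separate from gallstones, so the text appears misplaced. As it stands, G2 makes relief depend on the diet, while F3b associates gall bladder disease with caloric restriction and weight loss. The condition about keeping to the diet belongs only to the easing of discomfort; the claim that the risk is not serious and reversible is a separate, unconditional sentence.

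**3. What would be recorded.**
- *Event with a hospital or emergency visit:* asked about at each study visit and entered in the database (F2d, F3c). Any hospitalization also makes it serious under F3a and F3b. It is captured whatever G2 says.
- *Event without such a visit:* F3b monitors for gall bladder disease at each data collection visit and classes all events, and F2d reports all events. F3a records only serious events, with hyperglycemia as the stated less serious example. The sections give opposite answers.

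**4. Scale.** Inputs: n = 36 treated (C1) and risk p below 1% (G2). Assumption: p applies per participant over the study, with independent events.
- Expected cases at the bound: 36 × 0.01 = 0.36.
- P(at least one) = 1 − (1 − p)^36. At p = 1% this is 1 − 0.99^36 = 30.4%.
- Range for 36 treated: p = 0.1% gives 3.5%; 0.5% gives 16.5%; 2% gives 51.7%; 5% gives 84.2%. The last two lie above G2's bound.
- If the bound applied to all 72 participants: 72 × 0.01 = 0.72 expected cases, and P(at least one) = 51.5%.
- With zero cases in 36, the one-sided 95% upper limit is 1 − 0.05^(1/36) = 8.0%. A clean record could not confirm a risk below 1%.

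**The case against.** G2 is a description of risks, not an instruction for classifying or recording events. The protocol has several safeguards that work independently of it: questions about hospital and emergency care at each visit, hospitalization as a criterion for seriousness, and named monitoring for gall bladder disease. The recording gap for milder events comes from F3a against F3b and F2d, and applies to other non-serious events too. Listing gall bladder disease under both intervention and condition is not an error, since F3b says expectedness relates to both. All of this stands, and it limits the point to a drafting conflict plus a gap for milder events.

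A reader might go further in four ways that the documents do not support.
- *Consent is misleading.* The consent form is not in the reviewed text. G1 promises discussion of all potential risks and F2d a written list of side effects. The wording may or may not have been carried over.
- *The treatment-arm harm count is biased downward.* The recording rules are the same in both arms. Selective loss is possible but not shown.
- *One missed event would hide a signal.* At G2's bound, zero is the likeliest count, and this pilot could not interpret a single event.
- *The diet cannot be both cause and remedy.* That is a clinical argument. The text shows a tension that needs reconciling, not a logical impossibility.

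On the randomization bullet, the sentence continues with the possibility that the assigned treatment proves less effective than others, so it can be read as being about efficacy; and G2 itself lists hypoglycemia and gallstones as risks. It still reads poorly beside F2c, which says the intervention may raise the risk of hypo- and hyperglycemic episodes.

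**Conclusion.** The point holds in limited form. G2's blanket statement contradicts the outcome-based definition of seriousness in F3a and F3b, and its sentence on discomfort fits poorly with F3b's list. Separately, F3a conflicts with F3b and F2d on whether non-serious events are recorded, so a gall bladder event without a hospital or emergency visit may go unrecorded. The absolute numbers are small: at most 0.36 expected treated cases if G2's bound is right and applies per participant over the study. No bias in the arm comparison and no defect in the consent form is established. The change is worth making because it improves risk disclosure and safety capture at little cost.

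**What to change.** - **G2, gallstones:** delete the sentence on resolution within a week and the sentence on seriousness and reversibility. State that gall bladder disease is a listed risk of caloric restriction and weight loss (F3b), and refer to the F3a/F3b seriousness criteria. Give a source and time window for the risk below 1%.
- **Recording:** collect every gall bladder event in both arms, grade it by outcome, and apply one attribution rule to both arms. Do not presume relatedness from the assigned arm.
- **F3a, F3b and F2d:** reconcile them on whether non-serious events are recorded and reported.
- **G2, randomization bullet:** reconcile it with F2c.
- **Consent form:** check whether G2's wording was carried into it, and correct it if so.
- **Advice on the diet if gallstones occur:** this is a clinical matter on which G2 and F3b must be reconciled by those responsible.

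The cost is protocol wording (and consent wording if affected) through the IRB, plus one item collected at visits already planned. Design and sample size are unaffected.

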## K. Appendices
